1.5.4 Serum Progesterone Levels

In humans, progesterone is necessary for fertilization and maintenance of pregnancy (by maintaining myometrial relaxation).^{40,41} Progesterone is initially produced by the corpus luteum and from 7–8 weeks of gestation increasingly by the placenta. At term, in a singleton pregnancy, the placenta produces approximately 250–300 mg progesterone per day.⁴⁰ Prior to ovulation, serum levels are less than 1 ng/ml. Serum rise after ovulation for 6–10 days, then fall if fertilization does not occur. If a viable pregnancy occurs, serum levels rise throughout gestation. A characteristic of human pregnancy is that circulating progesterone levels do not fall with the onset of labor.

There is no data concerning fetal serum progesterone levels either during a normal pregnancy, or in response to exogenous progesterone. Although vaginal progesterone is commonly used for in conjunction with assisted reproductive technologies (ART) and to prevent preterm birth, there is very little data concerning placental levels, transplacental transfer or fetal blood levels. A study using ex vivo perfusion of placentas from term pregnancies showed that 17- α -Hydroxyprogesterone caproate is metabolized by placental lobules. Both the parent compound and the metabolites are transferred to the fetal circuit.⁶ There is no data on serum progesterone levels during pregnancy in mothers carrying a fetus with CHD. Uterine tissue concentrations of progesterone are significantly higher after vaginal administration than after systemic administration, despite higher blood levels with systemic administration.^{3,4} In a randomized trial, women undergoing hysterectomy received either vaginal or IM progesterone. The ratio of endometrial to serum progesterone concentrations was higher after vaginal administration of progesterone than after IM injections.³ The lower blood levels after vaginal administration have been associated with a lower prevalence of systemic side effects.^{3,5} Thus maternal serum progesterone levels after vaginal administration will not reflect endometrial or fetal serum concentrations.

1.5.5 Placental Function in Normal and CHD Pregnancies

The placenta is connected to the fetus by the umbilical cord and to the mother via the uterine wall. The umbilical cord contains two arteries and one vein. The placenta is primarily a vascular organ in which the uterine arteries bring maternal blood in contact with the placental villi in the intervillous space, where the trophoblastic epithelium surrounding the villi mediates the transfer of oxygen and other maternally-derived substances to the fetus. The normal placenta is long and thin, and contains numerous placental villi. The combination of a placental villous tree and its decidua is called a placentome (also a cotyledon). The diffusion barrier for transfer between mother and fetus is normally very small, made up by the trophoblast basement membrane and the fetal villous capillary endothelium. Fetal capillaries receive fetal deoxygenated blood and fetal waste products from arterioles arising from the umbilical arteries. Oxygenated and nutrient-enriched blood is returned to the fetus via a network of veins that drain into the umbilical vein. The maternal uterine arteries dilate significantly during the course of a normal pregnancy to increase maternal blood flow to the placenta and developing fetus; for example, 50 mL/minute of maternal blood enters the non-gravid uterus, increasing to approximately 700 mL/minute at near-term. This large increase is made possible by increased maternal blood volume, increased cardiac output, uterine artery dilation, and low uterine and placental vascular resistance. Appropriate placental functioning at the anatomic/histologic level of the placentome requires: 1) maternal uterine and decidua artery integrity, patency, flow, and dilation during pregnancy; 2) increased

maternal blood flow and low resistance through the intervillous space; 3) normal exposure of the villous trophoblastic endothelium to maternal blood; 4) low diffusion distance between maternal and fetal blood from the intervillous space across the trophoblast and villous endothelium; 5) integrity and patency of the villous vessels; 6) unobstructed flow in the umbilical cord.

There is increasing awareness of the importance of normal function and regulation of a placental synthetic, metabolic, and inflammatory functions to maintain placental integrity, maternal and fetal well-being, and normal fetal development. A variety of acute, sub-acute, and chronic abnormalities of placental anatomy and vascular function have been linked to maternal abnormalities such as preeclampsia and to fetal events such as fetal demise, IUGR, and perinatal brain injury; the types of injury have included white matter injury, stroke, or neonatal encephalopathy.⁷⁷⁻⁸⁰ Overall, associations between the development of early and mid-term placental abnormalities and subsequent events such as IUGR, stroke, preeclampsia, and abnormal post-natal brain anatomy and neurodevelopmental outcomes are increasing and becoming more firmly established. Despite this information, examination of the placenta—histopathological or otherwise—is not routine, even in pregnancies complicated by IUGR or early evidence of neonatal brain injury.

There is a significant lack of information about placental anatomy and function in infants born with CHD, despite the increased frequencies of IUGR, pre-term birth, relative brain immaturity, reduced brain size, and brain imaging abnormalities (prior to any cardiac or other interventions), etc. that occur in these infants. A recent study found significantly reduced fetal somatic growth velocity in the later stages of pregnancy as well as reduced birth weight in HLHS infants and suggested suboptimal energy balance due to placental vascular pathology as a potential cause.⁵¹ The increased risk of IUGR in fetuses with CHD was also suggested by a recent retrospective cohort study which found an approximately 2-to-3-fold increased risk of IUGR accompanied the fetal diagnosis of CHD (without chromosomal or extracardiac anomalies).⁷⁷ Preliminary data collected recently at CHOP suggests that various placental abnormalities with the potential to alter placental function and fetal homeostasis frequently occur in pregnancies complicated by CHD. Taken together, these data indicate that pregnancies complicated by fetal CHD may be at increased risk for abnormalities of placental anatomy and/or function that can compromise fetal growth and development and lead to increased risk of perinatal brain injury. Thus, a comprehensive and multimodal analysis of placental anatomy, vascularity, and biochemical function is warranted.

1.5.6 CHD and Preterm Birth

There is increasing evidence that even late preterm and early term birth is associated with worse perinatal and long-term neurodevelopmental outcomes in both the normal fetus and the fetus with CHD. In the fetus without CHD, there is significant neonatal morbidity associated with elective delivery at 37–38 weeks compared to deliveries occurring at 39–40 weeks.⁸¹ Neonatal death, respiratory complications, hypoglycemia, sepsis, seizures, necrotizing enterocolitis, hypoxic-ischemic encephalopathy, cardiopulmonary resuscitation or ventilator support within 24 hours after birth, umbilical-cord-blood arterial pH below 7.0, a 5-min Apgar of 3 or less, admission to the neonatal intensive care unit (NICU) and prolonged hospitalization of at least 5 days were significantly less likely to occur as gestational age increased from 37 (15.3%) to 39 weeks (8%), and plateaued at 40 weeks (7.3%).⁸¹ For the fetus without CHD, postponing elective delivery to 39 weeks may prevent 48% of cases of complications among deliveries at 37 weeks and 27% among 38-week deliveries.

Preterm birth is common for mothers carrying fetuses with CHD. Among 397 babies with CHD delivered in the Special Delivery Unit (SDU) at CHOP in fiscal years 2011 to 2013,

53% were delivered at < 39 weeks gestational age and 16% at \leq 37 weeks. Among 971 neonates treated at Boston's Children Hospital from 2002 through 2008, 56% were born at < 39 weeks gestational age and 19% at \leq 37 weeks.⁵² Data from the National Vital Statistics Report (<http://www.cdc.gov/nchs/data/nvsr/nvsr62/>) show that in 2011, among all births in the United States, 38% were at < 39 weeks gestational age and 12% were at < 37 weeks. These data suggest that the risk of preterm birth is increased for the fetus with CHD.

Late preterm or early term birth also has serious adverse effects for the fetus with CHD. Investigators from Boston Children's Hospital evaluated 971 consecutive neonates with CHD and a known gestational age born from 2002 through 2008.⁵² Compared with the referent group of neonates who were delivered at 39 to 40 completed weeks gestation, neonates born at 37 to 38 weeks had increased mortality (6.9% vs. 2.6%; adjusted P=0.049) and morbidity (49.7% vs. 39.7%; adjusted P=0.02) rates and tended to require a longer duration of mechanical ventilation (adjusted P=0.05). They concluded that for neonates with critical CHD, delivery before 39 weeks gestation is associated with greater mortality and morbidity rates and more resource use and that the ideal gestational age for delivery of these patients may be 39 to 40 completed weeks. Evidence from CHOP suggests that younger gestational age is associated with worse neurodevelopmental outcomes in children with CHD.⁵³ Neurodevelopmental outcomes were evaluated in 351 preschool children with CHD born at 36 weeks or greater gestational age. Performance for cognition, language, executive function, social skills, visual-motor, and fine-motor skills was better for those born at 39 to 40 weeks of GA or more versus those born at less than 39 weeks (all P<.05). These findings are consistent with the hypothesis that delivery before 39 to 40 weeks gestational age is associated with worse outcomes in patients with CHD. Early delivery of a child with CHD is often indicated because of maternal or fetal health issues. In the absence of these concerns, these data suggest that elective (or spontaneous) delivery at 39 to 40 weeks gestational age is associated with better neurodevelopmental outcomes.

The reasons for an increased incidence of preterm birth for fetuses with CHD have not been fully delineated. Early delivery is sometimes required for maternal or fetal health issues. However, there is evidence that placental structure and function are often abnormal in pregnancies where the fetus has CHD, which may contribute to the risk of preterm birth. Preliminary data from CHOP shows that there are multiple abnormalities in the placenta of the fetus diagnosed with CHD, which may impact growth and development, timing of delivery and long-term outcomes such as neurodevelopment and late vascular health. Placentas from 72 pregnancies were examined. Insertion of the umbilical cord into the placenta was eccentric in 61 (84%) and velamentous in 3 (4%). Abnormal maturation of villi was present in 29%; chorioangiosus in 14%. An abnormal fetal/placental weight ratio (as compared to published norms) was seen in 46%. Evidence for inflammation was present overall in 19% and vascular thrombosis in 16%. Infarction was present overall in 14%, but most commonly in HLHS and TGA (25%). There is evidence that the fetus with CHD is at increased risk for intra-uterine growth retardation (IUGR), which may be due in part to uteroplacental insufficiency.⁷⁷ In a retrospective cohort study of 67,823 patients, there were 193 cases of fetal CHD (0.3%) and 5,669 cases of IUGR (8.4%). Prenatal diagnosis of CHD was associated with an increased risk of IUGR (23.8% vs. 8.5%, adjusted odds ratio [aOR] 3.3, 95% confidence interval [CI] 2.4–4.6), and the risk was greatest in fetuses with major CHD (16.5% vs. 8.5%, aOR 2.1, 95% CI 1.3–3.2).⁷⁷ Isolated CHD was also associated with an increased risk of IUGR (17.8% vs. 8.5%, aOR 2.2, 95% CI 1.4–3.7). The increased risk persisted after excluding extracardiac and chromosomal anomalies. There was a significantly increased incidence of single umbilical artery in fetuses with CHD, consistent with structural placental abnormalities. There is no data concerning progesterone levels and metabolism in pregnancies with a fetus with

CHD. Overall, the existing data suggest that pregnancies with CHD are at increased risk for uteroplacental insufficiency and may be considered stressed or compromised pregnancies.

1.6 COMPLIANCE STATEMENT

This study will be conducted in full accordance all applicable Children's Hospital of Philadelphia Research Policies and Procedures and all applicable Federal and state laws and regulations including 45 CFR 46, 21 CFR Parts 50, 54, 56, 312, 314 and 812 and the Good Clinical Practice: Consolidated Guideline approved by the International Conference on Harmonization (ICH). All episodes of noncompliance will be documented.

The investigators will perform the study in accordance with this protocol, will obtain consent and assent, and will report unanticipated problems involving risks to subjects or others in accordance with The Children's Hospital of Philadelphia IRB Policies and Procedures and all federal requirements. Collection, recording, and reporting of data will be accurate and will ensure the privacy, health, and welfare of research subjects during and after the study.

2 STUDY OBJECTIVES

We propose a Phase II single-center placebo-controlled randomized therapeutic exploratory trial to determine whether there is evidence that progesterone, administered prenatally, improves neurodevelopmental outcomes, improves brain development, and reduces perioperative white matter injury in neonates with CHD undergoing cardiac surgery. The data provided by this therapeutic exploratory study will aid in selection of appropriate outcomes and inform sample size calculations for a future multi-institutional study.

2.1 Primary Objective (or Aim)

Primary Aim: Develop preliminary evidence to support a multi-institutional study to determine whether, in women carrying fetuses with CHD (maternal-fetal dyad), prophylactic vaginal natural progesterone therapy is neuroprotective, and compared to placebo improves neurodevelopmental outcomes at 18 months of age.

Hypothesis:

Compared to placebo, progesterone administration results in a higher score on the Motor Scale of the Bayley Scales of Infant and Toddler Development-III (Bayley-III) at 18 months of age.

2.2 Secondary Objectives (or Aims)

Specific Aims: Develop preliminary evidence to support a multi-institutional study to determine whether, in women carrying fetuses with CHD (maternal-fetal dyad), prophylactic vaginal natural progesterone therapy is neuroprotective, and compared to placebo:

1. improves fetal brain growth and maturation,
2. increases myelination during fetal brain development,
3. reduces pre-operative brain white matter injury, and
4. reduces post-operative white matter injury.

Hypotheses:

Compared to placebo, progesterone administration results in

1. higher scores on the Cognitive and Language Scales of the Bayley Scales of Infant and Toddler Development-III (Bayley-III) at 18 months of age,

2. a higher total maturation score (TMS) on early post-natal MRI,
3. Increased global and regional brain volumes
4. a greater volume of myelinated white matter (VMWM) in the posterior limb of the internal capsule on early post-natal, pre-operative MRI,
5. lower periventricular leucomalacia (PVL) volume on early post-natal, pre-operative MRI,
6. lower PVL volume on post-operative MRI.

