
glial cell oligodendrocytes in the CNS and play an important role in the formation of myelin sheaths. Progesterone has also been shown to increase myelination and enhance maturation of immature oligodendrocytes progenitor cells to mature oligodendrocytes, which are more resistant to hypoxic/ischemic injury. Therapeutic administration of progesterone has also been demonstrated to prevent preterm birth. Thus, there are two potential mechanisms by which pre-natal progesterone therapy may improve neurodevelopmental outcomes in neonates with CHD: 1) a direct neuroprotective effect, and 2) decreasing the occurrence of pre-term birth.

Study Objective(s)	
Primary
 
Develop preliminary evidence to support a multi-institutional study to determine whether, in women carrying fetuses (maternal-fetal dyad) with CHD, prophylactic vaginal natural progesterone therapy is neuroprotective, and compared to placebo improves neurodevelopmental outcomes at 18 months of age.
 
Secondary
 
Develop preliminary evidence to support a multi-institutional study to determine whether, in women carrying fetuses (maternal-fetal dyad) with CHD, prophylactic vaginal natural progesterone therapy is neuroprotective, and compared to placebo:
 
 1. improves fetal brain growth and maturation, 2. increases myelination during fetal brain development, 3. reduces pre-operative brain white matter injury, and 4. reduces post-operative white matter injury.
Test Article(s) (If Applicable)	Prophylactic vaginal natural progesterone (90 mg as an 8% vaginal gel BID) from 24–39 weeks gestation, compared to placebo.
Study Design	Phase II single-center placebo-controlled randomized therapeutic exploratory trial.
Subject Population key criteria for Inclusion and Exclusion:	
Inclusion Criteria
 
Mother carrying a fetus with CHD (maternal-fetal dyad) requiring surgery with cardiopulmonary bypass (CPB) prior to 44 weeks corrected gestational age (GA) identified prior to 28 weeks GA.
 
Exclusion Criteria
 
 1. Major genetic or extra-cardiac anomaly other than 22q11 deletion 2. Language other than English spoken in the home 3. Known sensitivity or listed contraindication to progesterone (known allergy or hypersensitivity to progesterone, severe hepatic dysfunction, undiagnosed vaginal bleeding, mammary or genital tract carcinoma, thrombophlebitis, thromboembolic disorders, cerebral hemorrhage, porphyria)

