3.1.3 Post-Natal Phase

After birth, the child will undergo clinically indicated evaluation and treatment. Data will be collected from the medical record concerning diagnosis, associated anomalies, medical and surgical management and the hospital course. A blood (either from the cord or from an existing blood drawing line during a hospitalization, routine clinical labwork or at the time of a research draw for a separate study) or saliva sample will be obtained for genetic testing. An early post-natal brain MRI will be obtained on the day of cardiac surgery, during the same anesthetic but prior to surgery. Post-operative brain MRI will be obtained within 10 days of surgery.

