5.2.4 Fetal Brain MRI

Prenatal MRI examinations will be performed once at 25-28 weeks GA and once at 34-36 weeks GA.

The prenatal MRI sequences will include:

1. T2 weighted images including half-Fourier acquisition single shot turbo spin echo T2 images in axial, sagittal, and coronal planes.
2. Echoplanar images at short and long TE to assess for hemorrhage.
3. T1 fast low angle shot images (if bleeding or clotting is suspected on other images)
4. Magnetic resonance spectroscopy.
5. Diffusion imaging.

Analysis of the fetal Brain MRI examinations will include:

1. Evaluation for anatomic abnormalities (malformations) and in-utero gross insults.
2. Size of ventricles.
3. Assessment of hemorrhage.
4. Fetal total maturation score (fTMS) evaluation which assesses myelination, cortical folding, and the germinal matrix evolution.
5. Assessment of brain volumetrics.
6. MR spectroscopic assessment of choline, N-acetylaspartate, lactate, and creatine metabolites, including corresponding ratios.

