Statistical Analysis Plan
Randomized Trial of Maternal Progesterone Therapy to Improve
Neurodevelopmental Outcomes in Infants with Congenital Heart Disease.

J. [name], Principal Investigator
[name], PhD, ScD, Statistician

ClinicalTrials.gov identifier (NCT number): [NCT02133573](#)

Sponsor: Children's Hospital of Philadelphia

Version Date: 3/7/2022

Design: Randomized phase II 2-arm trial design

Control: Vaginal lubricant, twice a day

Intervention: Vaginal gel, 90mg twice a day

Consort Diagram: Per recommendations. <http://www.consort-statement.org/consort-statement/flow-diagram>

Primary Endpoint

The primary endpoint is the Motor Scale of the Bayley-III at 18 months of age.

Secondary Endpoints (Pre-specified in the protocol)¹

Secondary endpoints pre-specified in the protocol are:

1. Developmental (Bayley-III at 18 months of age)
 - a. Cognitive Scales
 - b. Language Scales
 - c. Fine motor score
 - d. Gross motor score
 - e. Receptive Communication
 - f. Expressive Communication
2. Adherence to study protocol
 - a. Progesterone regime (Average adherence by medication return and by diary)
 - b. Complete pre- and post-natal MRI's
 - c. Complete 18-month neuro-developmental evaluation
3. MRI-based
 - a. Total maturation score (TMS) on Pre-operative MRI
 - b. Brain volumes on Preoperative MRI:
 - i. Whole Brain
 - ii. Cerebellum
 - c. White Matter Injury
 - i. Volume on early post-natal brain MRI
 - ii. Volume on early post-operative brain MRI
 - iii. Volume change from pre-operative to post-operative brain MRI.

‘Secondary’ endpoints (Post Protocol) As clinical practice and research findings regarding progesterone use during pregnancy evolved over the course of accrual to the trial, these new secondary endpoints were identified. They were prespecified prior to closure of the database, and while the principal investigator and research team, other than [name] and [name] (statistical analyst), were blinded. They include;

1. Fetal Variables: Fetal echocardiogram and OB ultrasound Doppler flows (umbilical artery, uterine artery, middle cerebral artery, oligohydramnios, fetal growth restriction (BW < 10th percentile))
2. Maternal Complications: (gestational hypertension, preeclampsia, abruption, , gestational DM, maternal tobacco use, maternal hypothyroidism)

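### The aims on the fetal brain have no planned between-arm comparison at the 34-36 week fetal MRI; TMS and brain volumes are compared on the day of surgery, where faster maturation cannot be separated from later birth

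*Protocol*

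**What the plan says.** **Aims.** Protocol section 2.2 asks whether progesterone "improves fetal brain growth and maturation" (aim 1) and "increases myelination during fetal brain development" (aim 2).

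**Hypotheses (same section).** For TMS: "a higher total maturation score (TMS) on early post-natal MRI". Volume of myelinated white matter (VMWM) is also tied to the early post-natal, pre-operative scan. The volume hypothesis, "Increased global and regional brain volumes", names no scan.

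**Endpoints.** Protocol section 6.2 lists TMS and volumes without naming a scan. The SAP's pre-specified list does name one: "Total maturation score (TMS) on Pre-operative MRI", with whole-brain and cerebellar volumes on the same MRI. SAP Efficacy Analysis item 4 compares them by the two-sample t method used for the primary endpoint. VMWM is not itemised in the SAP's secondary list.

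**Timing of the post-natal scan.** Section 3.1.3: "An early post-natal brain MRI will be obtained on the day of cardiac surgery, during the same anesthetic but prior to surgery".

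**Expected mechanisms.** The Synopsis rationale names two: "1) a direct neuroprotective effect, and 2) decreasing the occurrence of pre-term birth". Section 1.4 gives fewer births before 39 weeks as one reason for treating to 39 weeks.

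**Fetal scans.** Section 5.2.4: "Prenatal MRI examinations will be performed once at 25-28 weeks GA and once at 34-36 weeks GA". Read-outs include fTMS and volumetrics. The Abstract lists both fetal scans under main outcome measures and puts the first before randomisation. SAP post-protocol item 9 covers trajectories of volumes and TMS from fetal to first post-natal MRI, without saying which fetal scan or giving an analysis.

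**The concern.** The aims ask what happens to the brain before birth, but the pre-specified TMS and volume comparisons are made after birth, at an age the design does not fix. Postmenstrual age at the pre-operative scan is gestational age at birth plus age at surgery, and the first of these is something the protocol hopes treatment will change. If maturation score and volume rise with age, a higher mean in the progesterone arm could reflect faster maturation, a brain scanned later because birth was later, or both.

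The protocol says the trial is meant to help choose outcomes for a multi-institutional study. That choice depends on which of the two mechanisms produced any difference. A scan before delivery, in a two-week gestational window and with a pre-randomisation scan for comparison, bears on this directly. It is collected, but no analysis of it by arm is planned.

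**Working it through.** **1. Where each scan appears.**

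| Place | Pre-operative MRI | 34-36 week fetal MRI |
|---|---|---|
| Protocol 2.2 hypotheses | TMS, VMWM | none (volume hypothesis names no scan) |
| Protocol 6.2 endpoints | not specified for TMS or volumes | not specified |
| SAP pre-specified endpoints | TMS, whole brain, cerebellum | none |
| SAP Efficacy Analysis item 4 | t-interval or t-test by arm | none |
| SAP post-protocol item 9 | end of trajectory | implied at most; scan and method not stated |
| Abstract, main outcome measures | listed | listed |
| Protocol 5.2 read-outs | TMS, volumes including VMWM | fTMS, volumetrics |

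Item 9 does not fill the gap. It ends at the post-natal scan, so it carries the same dependence on age at birth and surgery. The scores also differ at its two ends: section 5.2.4 builds fTMS from myelination, cortical folding and germinal matrix, while section 5.2.5 adds migrating bands to the post-natal TMS.

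**2. The plan's precision for TMS.** Half-width of the 90% interval = t(0.95, 2n-2) x SD x sqrt(2/n), with SD 1.32 (section 6.4):

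- n = 40: 1.665 x 1.32 x 0.2236 = 0.49 (Table 1 of section 6.4: 0.49)
- n = 50: 1.661 x 1.32 x 0.2000 = 0.44 (Table 1: 0.40)
- n = 60: 1.658 x 1.32 x 0.1826 = 0.40 (text: 0.44)

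The n = 40 figure reproduces. The stated n = 50 and n = 60 figures look interchanged. I use 0.40 for n = 60.

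**3. What age at scan alone could do.** The documents give neither a TMS slope per week nor an expected shift in gestational age, so both inputs are assumptions.

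- Difference d = slope x shift. A slope of 0.1 to 0.5 points per week and a shift of 0.25 to 1.5 weeks give d from 0.025 to 0.75.
- Standard error = 1.32 x sqrt(2/60) = 0.241.
- Chance that a two-sided 10% test is significant, by normal approximation: Φ(d/0.241 - 1.645) + Φ(-d/0.241 - 1.645).

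| Slope (per week) | Shift (weeks) | d | Chance of significance |
|---|---|---|---|
| 0.1 | 0.25 | 0.025 | 0.10 |
| 0.2 | 0.5 | 0.10 | 0.13 |
| 0.3 | 1 | 0.30 | 0.35 |
| 0.5 | 1 | 0.50 | 0.67 |
| 0.5 | 1.5 | 0.75 | 0.93 |

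These are not Type I error rates for the randomised comparison. If treatment delays birth, d is a real effect of treatment. The table shows how often a significant result could arise with no direct effect on maturation.

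**4. Room for a shift.** Section 1.5.6 reports that 53% of 397 babies with CHD at this centre were delivered before 39 weeks. A shift is therefore possible, but nothing in the documents sizes it.

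**The case against.** A reader might infer that the fetal aims are tested only after birth and that the 34-36 week MRI is not an outcome at all. The documents do not support that. The Abstract lists the scan under main outcome measures (a list made up largely of procedures), section 5.2 places it among the efficacy evaluations, the volume hypothesis names no scan, and SAP item 9 uses fetal MRI. What is missing is narrower: a stated comparison of the arms at that scan.

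A reader might also call the pre-operative TMS comparison biased, or an age-driven difference an artefact. That does not follow. Later birth is one of the two stated mechanisms, so the comparison estimates the total randomised effect. It is also a reasonable choice: section 1.5.2 links brain maturity before surgery to injury risk, and immaturity at surgery to outcome at two years.

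Nor is it a fault that SAP item 7 leaves out the gestational age and age-at-surgery terms listed in protocol section 6.3.2. Gestational age at birth and age at surgery arise after randomisation, and item 7 is an adjustment for baseline covariates.

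Three further objections stand as limits:

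- VMWM is not a listed fetal read-out, and fetal T1 imaging is reserved for suspected bleeding or clotting. For aim 2 the fetal scan offers only the myelination component of fTMS.
- Study drug may continue to 39 weeks, so a scan at 34-36 weeks misses up to 3 to 5 weeks of exposure.
- Section 1.3.3 cites delayed parturition mainly in women with a short cervix and possibly those with prior preterm birth. Section 3.4.2 excludes women with prior preterm birth or a short cervix needing progesterone, so the shift may be small here.

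**Conclusion.** The point holds in a limited form. The pre-specified TMS and volume comparisons answer whether the brain is more mature at surgery. They cannot show how much of any difference is faster fetal maturation and how much is later birth. The scan best placed to help has no planned comparison between arms.

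The size cannot be set from the documents. Under the assumed ranges, the age-driven TMS difference runs from negligible (0.025) to nearly twice the 0.40 half-width (0.75). It exceeds the half-width only towards the upper end of both assumptions.

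The gap concerns interpretation of secondary endpoints in an exploratory phase II trial. The primary Bayley-III Motor analysis is untouched. It is still worth correcting, because choosing outcomes for the next trial is a stated purpose and the scans are already scheduled.

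**What to change.** In the SAP:

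1. Add a secondary endpoint for aim 1: fTMS and total and regional brain volumes at the 34-36 week fetal MRI. Compare arms by linear regression with gestational age at scan and the pre-randomisation fetal MRI value as covariates, and report the 90% interval.
2. Label this supportive for aim 2, through the myelination component of fTMS only.
3. Keep pre-operative TMS and volumes as the total effect at surgery, and word that conclusion as maturation at surgery. Report postmenstrual age at the scan by arm. The SAP already lists age at birth and age at first operation among its post-protocol endpoints, so little is added.
4. Do not adjust the pre-operative comparison for gestational age at birth or age at surgery as though they were baseline covariates.
5. In post-protocol item 9, name the fetal scan and the method, and say how fTMS and TMS are put on a common footing.

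The cost is SAP wording and one analysis of planned read-outs. Fetuses delivered before the 34-36 week scan are not included, so report their number by arm; exposure after that scan is not captured. If the addition is made after unblinding, label it post hoc.
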